5.9.4. Returning IP

Do not return IP to Rebiotix. For IP received but not administered to a subject, it must be destroyed by site staff per the institution's processes. Destruction must be recorded on the Product Accountability Log.

5.9.5. Product Accountability and Tracking

Each unit of IP is sent to the site for administration to an assigned subject and is labeled with a batch number to be recorded in the eCRF and on the Product Accountability Log. Each unit must be tracked on the Product Accountability Log by the person(s) authorized on the Delegation of Authority Log to perform that step. IP must be kept in a secure location under the control of the site investigator or authorized designee as recorded on the Delegation of Authority Log. The Product Accountability Log and Delegation of Authority Log are to be maintained by the site and confirmed during

monitoring visits. The steps to be tracked include dates of receipt and dispensing, batch number, subject number, storage in refrigerator, and destruction if not administered to a subject. The IP Administrator must ensure the correct batch number is administered to the correct subject.

6. Study Procedures

6.1. General Information

Study information is collected on study-specific electronic case report forms (eCRFs) by the site. Study monitoring occurs at regular intervals to ensure the protection of subject rights and safety, data integrity and accuracy, and proper study conduct in compliance to the protocol and applicable regulations including 21 CFR 312 and ICH E6 GCPs. Study visits and telephone assessments must occur with the window specified in Table 6-1; visits and calls out of window or missed are to be reported as protocol deviations. The study-required procedures are to be conducted as shown in Table 6-1.

Table 6-1 Schedule of Events

Activity	Screening (Enrollment)	Baseline / Enema Administration (\leq 21 days from screening)	Follow-up Visits 1-, 4- and 8- Week (\pm 3 days) Assessments ¹	Weekly Phone Assessment (Weeks 2, 3 and 6 (\pm 3 days))	Unscheduled Possible Recurrence Visit	Unblinded Enema Administration ¹ (\leq 21 calendar days post Tx Failure)	Phone Assessment at 3 and 6 months (\pm 14 days)
Informed consent obtained	X						
Demographics, medical history	X						
Prescribe/continue antibiotics for CDI symptom control	X						
Modified physical exam conducted		X					
Stool sent to Rebiotix by subjects for testing and archiving (optional)	X		X		X		X
Central Lab CBC w/differential testing ³	X ³	X					
Central Lab CMP & CRP testing	X						
C. difficile testing ⁴	X ⁴				X ⁴		
Central Lab stool and blood testing		X					
Urine pregnancy testing performed at site (if applicable)	X	X				X	
Cdiff32 Questionnaire	X		X		X		X
Inclusion/exclusion criteria confirmed	X	X					
Randomization assignment	X ⁵						
24-72hr washout period confirmed		X				X	
Enema administered		X				X	
Product complaint (if applicable)		X				X	
Recurrence or New CDI symptoms assessed		X	X	X	X	X	X
Vital signs assessed	X	X			X	X	
Subject Diary discussed/reviewed	X	X	X ⁶			X	
Employment status assessed	X		X ⁷				X
Concomitant medications	X	X	X	X	X	X	X
Medical History Assessment	X		X ⁷		X		X
Adverse events assessed		X	X	X	X	X	X
Solicited events assessed ²		X	X ²			X ²	
Protocol deviations (if applicable)	X	X	X	X	X	X	X

¹ Documented treatment failures may receive an unblinded RBX2660 enema. If an unblinded enema is administered, the follow-up visit requirement re-start based on the date of last enema administration.

² Solicited events are collected in the Subject Diary from the day of administration of any study enema (blinded or unblinded) until the day prior to the 1-week visit. The Subject Diary is collected and reviewed at the 1-week visit. Solicited events that increase in severity from screening should be assessed for a possible adverse event.

³ Exclusion criteria for absolute neutrophil count should be assessed based on the CBC collected at the screening visit.

⁴ Perform within 30 days prior to or at enrollment and if CDI recurrence is suspected.

⁵ Randomization should occur after screening criteria have been assessed and eligibility confirmed (4-14 calendar days from randomization to blinded study treatment).

⁶ Subject Diary is reviewed only at the 1-week follow-up visit.

⁷ Collected at the 8-week follow-up visit only.

6.2. Informed Consent

All subjects must sign the study-specific IRB/REB-approved Informed Consent/HIPAA Form; see Section 4.3. The original signed Form is to be placed in the subject's study file. A copy of the signed Form is also to be given to the subject for his/her records.

6.3. Subject Diary

The Subject Diary serves as a tool for the subject to record pre- and post-treatment health and information that may indicate adverse events or the recurrence of CDI. The subject also documents changes in medications.

At the time of enrollment (informed consent) subjects are provided a Subject Diary that they are to complete until the day prior to the blinded study enema. This may mean up to 21 days depending on how long it takes to determine subject eligibility for the study. The diary will be collected and reviewed at the baseline visit prior to enema administration.

A diary is also given to the subject on the day of the blinded study enema administration and is collected at the 1-week office visit. The Subject Diary is reviewed for solicited event occurrence and severity, changes to medications, occurrence of adverse events, and possible recurrence of CDI. The following information is entered into the study database:

- solicited event severity
- changes to medication
- occurrence of adverse events

If a subject is a documented treatment failure and s/he elects to receive unblinded RBX2660 treatment, the follow-up visit requirements start over with the receipt of an unblinded enema. The subject will be given additional diary pages to complete beginning on the day of the unblinded enema until the 1-week visit. This additional information is also entered into the study database.

6.4. Optional Stool Samples for Additional Testing by Rebiotix

Subjects are requested to provide stool samples directly to Rebiotix at:

- Screening (between the time of enrollment and prior to treatment)
- at the time of the 1, 4 and 8 week office visits;
- at the time of the 3 and 6 month phone calls;
- at the time of possible treatment failure symptoms.

Subjects collect the samples at home in pre-labeled containers given to them by the study team. Rebiotix provides the study sites with kits containing all the materials for collecting and shipping the samples, including subject directions, container labels, and prepaid, preaddressed mailing labels. Samples are identified by the label on the container that contains only the subject's study identification number and date/time of the sample; samples will not contain any personal information that would identify the subject. Samples may be stored for approximately five years. The stool samples will be used for research about the microorganisms in the human gut. Some of the research will include testing for microorganisms (*Clostridium difficile* and vancomycin-resistant enterococcus) both before and after receiving the study enema. Failure to send in a sample does not require a protocol deviation, however subjects should be reminded of this request.

6.5. Screening Visit

The following study activities/data will be collected at the screening visit:

- Subjects are told about the study and informed consent is obtained (enrollment)
- Standard demographics (gender, ethnicity, date of birth, race.)
- Detailed medical history, including Charlson Comorbidity Index variables
- Assess inclusion/exclusion criteria, including *C. difficile* stool testing
 - At the time of enrollment or study entry, a positive stool test for toxigenic *C. difficile* must be or have been performed and documented no more than 30 days before entry and must be on file at the site. *C. difficile* laboratory testing according to the site's standard of care is acceptable for enrollment, however, the use the C. DIFF QUIK CHEK COMPLETE® Test rapid enzyme immunoassay test for enrollment is preferred. If the rapid enzyme immunoassay test is utilized, the same interpretation of results as defined for treatment failures is required.
- Core laboratory blood sample is collected for CBC w/differential and comprehensive metabolic panel (CMP: Sodium, potassium, chloride, BUN, creatinine, albumin, AST, ALT, alkaline phosphatase, bilirubin (direct, indirect and total), glucose) and C-reactive protein (CRP) testing
- Onsite urine pregnancy test for subjects of child bearing potential
- For subjects who consented to the Optional Stool Sample collection, remind them to obtain and ship a stool sample to Rebiotix anytime between their enrollment date and their blinded enema administration visit
- Assess vital signs: height, weight, temperature, blood pressure, pulse, respiration.
- Complete the Cdiff32 health-related quality of life questionnaire

- Document concomitant medications
- Completion of the Subject Diary is explained and how to complete it is demonstrated; see Section 6.3.
- Verify employment status
- Assess for protocol deviations

6.6. Randomization

Once enrolled (informed consent obtained), in order to be randomized and treated:

1. Subject must meet all of the inclusion and none of the exclusion criteria;
2. Antibiotics will have been administered for a minimum of 10 consecutive days prior to the washout period;
3. CDI symptoms must be under control leading into the antibiotic washout period.

After enrollment and confirmation of inclusion/exclusion criteria compliance, including criteria confirmed by central laboratory testing, the study coordinator or other trained and authorized site staff randomize the subject in the Interactive Response Technology (IRT) System and ensures study treatment is completed within 4-14 calendar days of randomization. Ultimately, the study treatment needs to be administered within 21 days of the Screening visit.

The randomization schedule will be created using randomized blocks within four strata based on antibiotics used at screening (Vancomycin alone, Vancomycin in combination, Fidaxomicin or Other), and randomized subjects will be assigned one of two treatments (Group A or Group B) within the appropriate stratum. The randomization will not be stratified by site, so each site will draw from the same set of blocks. A subject will be assigned the next available treatment allocation from the randomization list. The randomization code and the date and time of randomization will be captured in the IRT.

Enrolled (consented) subjects who are randomized but exited prior to attempting the blinded treatment may be re-enrolled if another CDI recurrence occurs and thus randomized under a different subject identification numbers (re-randomized). If this occurs, they will be included in the analysis using their second randomization assignment and subsequent assessments and will only be counted once towards the total randomized.

Treatment will be assigned in the following proportions: 2:1 to yield a total of up to 270 randomized and treated subjects, or approximately 180 subjects randomized to treatment with RBX2660 and 90 subjects randomized to Placebo. Subjects who are randomized but exit prior to the administration of the first blinded enema may be replaced with additional subjects which could cause overall number of subjects randomized to be greater than the 270 anticipated, however no more than 270 subjects will be treated with

a blinded enema. The assignment is transmitted to the Rebiotix Operations Department, who will ship the correct IP to the site for each treatment. Replacement subject will also be randomized to ensure proper blinding.

6.7. Baseline Visit and Enema Administration

The baseline visit is performed on the day of the blinded enema administration. Randomization and IP administration must occur within 21 days of the screening visit. Antibiotics for the control of CDI symptoms are prescribed or continued until 24-72 hours before administration of the blinded study enema.

The following study activities/data will be collected at the baseline visit prior to enema administration:

- Inclusion/exclusion criteria are confirmed including the following:
 - The control of symptoms during antibiotic use is confirmed by review of the subject diary
 - Compliance to the washout period (discontinuation of the antibiotics for 24-72 hours prior to the baseline visit) is confirmed
- Modified physical exam (no genitourinary exam unless medically indicated) is performed to establish baseline health status (findings that can be attributed to the subject's medical history will not be documented as adverse events)
- Central laboratory blood sample collection for CBC w/differential, HIV, Hepatitis A (IgG) Hepatitis B Anti-Hepatitis B surface antigen, Hepatitis C antibody, and Treponema Antibody. *NOTE: the results are **not** needed before proceeding to treatment per the protocol*
- Central laboratory stool sample is collected. *NOTE: the results are **not** needed before proceeding to treatment per the protocol*
- Onsite urine pregnancy test for subjects of child bearing potential
- Assess vital signs: temperature, pulse, blood pressure, respiration
- Changes to concomitant medications since the last visit
- Review subject diary
- Assess recurrence of CDI
- Assess for adverse events since enrollment
- Assess for protocol deviations

Following successful completion of the baseline visit, investigational product is then administered via enema per the Instructions for Use and standard site procedure by the authorized IP Administrator; see Section 5.9.3. Subjects remain at the site under supervision for at least one hour post-IP administration for vital sign assessment (temperature, heart rate, blood pressure, respiratory rate) about every 15 minutes and

observation. If the subject's vital signs do not return to the pre-administration values ± 20%, assess the subject for a possible AE. The subject is sent home after completion of study procedures and a review of the Subject Diary instructions, and is requested to call the study coordinator if symptoms recur or at the onset of an adverse event.

Table 6-2: Subject Baseline Stool and Blood Testing Conducted by Central Laboratory

Test Name	Material Tested
Norovirus	Stool
Rotavirus	
Adenovirus	
Enteric pathogens (Shigella , Salmonella , Campylobacter , sorbitol-negative E. coli ., Aeromonas , Plesiomonas , Yersinia , and shiga toxins)	
Giardia antigen	
Cryptosporidium antigen	
Acid-fast staining (Cyclospora , Isospora)	
Ova and parasites	
Vancomycin-resistant enterococci (VRE)	
Methicillin-resistant Staphylococcus aureus (MRSA)	
Vibrio	
Listeria	
Clostridium difficile	
Carbapenem-resistant Enterobacteriaceae Culture (CRE)	
CBC with Differential	Blood
HIV	
Hepatitis A (IgG)	
Hepatitis B Anti-Hepatitis B surface antigen	
Hepatitis C Antibody	
Treponema Antibody	

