5.4. Treatment Regimen

Randomization is to occur about 4-14 calendar days prior to the blinded study treatment to allow for notification to Rebiotix and shipment of product. Ultimately, the study treatment needs to be administered within 21 days of the Screening visit. Subjects are randomized to one of the following groups:

- Group A: Placebo
- Group B: RBX2660

Randomization will occur in a 2:1 fashion with two subjects randomized to receive RBX2660 for every one subject randomized to Placebo.

Once completed, assigned study treatment consists of a single blinded enema of either RBX2660 or Placebo as per the randomization assignment. Product is to only be administered by the authorized IP Administrator who must be a qualified and trained health care professional following the Instructions for Use and standard site procedures. Subjects are to remain at the site under supervision for at least one hour post-enema administration for vital sign assessment (temperature, heart rate, blood pressure, respiratory rate) and observation.

Subjects with a documented treatment failure following blinded treatment may be scheduled for administration of an unblinded RBX2660 enema. In order to receive an unblinded RBX2660 enema, a subject must have documentation of meeting all treatment failure criteria as defined by the protocol (Section 3.7).

If, in the opinion of the investigator, antibiotics are warranted for the control of CDI symptoms prior to receiving the unblinded RBX2660 enema, they can be administered but need to be stopped 24-72 hours before enema administration. The total time from a treatment failure (CDI recurrence) determination to administration of an unblinded enema is within 21 calendar days.

See Section 6 for the Schedule of Study Procedures and detailed description of the requirements.

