7.1. Adverse Event Management

Adverse events, which include clinical laboratory test variables, will be monitored and documented from the time of informed consent. Subjects should be instructed to report any adverse event that they experience to the investigator. Investigators should make an assessment for adverse events at each visit and record the event on the appropriate eCRF.

Wherever possible, a specific disease or syndrome rather than individual associated signs and symptoms should be identified by the investigator and recorded on the eCRF.

However, if an observed or reported sign or symptom is not considered a component of a specific disease or syndrome by the investigator, it should be recorded as a separate adverse event on the eCRF. Additionally, the condition that led to a medical or surgical procedure (e.g., surgery, endoscopy, tooth extraction, or transfusion) should be recorded as an adverse event, not the procedure.

Any medical condition already present at screening should not be reported as an adverse event unless the medical condition or signs or symptoms present at baseline changes in severity or seriousness at any time during the study. In this case, it should be reported as an adverse event.

Clinically significant abnormal laboratory or other examination (e.g. electrocardiogram) findings that are detected during the study or are present at screening and significantly worsen during the study should be reported as AEs. The investigator will exercise his or her medical and scientific judgment in deciding whether an abnormal laboratory finding or other abnormal assessment is clinically significant. Clinically significant abnormal laboratory values occurring during the clinical study will be followed until repeat tests return to normal, stabilize, or are no longer clinically significant. Any abnormal test that is determined to be an error does not require reporting as an AE.

Recurrence of CDI is not to be reported as an AE unless hospitalization \geq 24 hours is required to treat it. If a hospitalization of \geq 24 hours is not required, it is to be recorded on the Follow-up eCRF and applicable CDI Form which will be reviewed as a component of the efficacy assessment. If hospitalization \geq 24 hours is required, it is to be reported as an SAE.

Adverse events should be followed until the event resolves or the subject exits the study. Events lasting > 3 months are considered to be chronic in nature.

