7.4. Solicited Events

The following list of anticipated events are solicited from subjects via the Subject Diary:

- gas (flatulence)
- abdominal distension or bloating
- rectal irritation or pain
- chills/severe shivering
- abdominal pain or cramping
- increased diarrhea
- constipation
- rectal bleeding
- nausea
- vomiting
- fever $\geq 37.8^{\circ}$ C (100.0°F)

Through the completion of the Subject Diary, subjects are asked specific questions regarding frequency and severity of the solicited AEs.

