Abdominal cramping/pain	Discomfort/pain causing no or minimal interference with usual social and functional activities	Discomfort/pain causing greater than minimal interference with usual social and functional activities	Discomfort/pain causing inability to perform usual social and functional activities	Disabling pain causing inability to perform basic self-care OR inpatient hospitalization \geq 24 hours
Constipation	Occasional or intermittent symptoms, occasional use of stool softeners, laxatives, dietary modifications or enema	Persistent symptoms with regular use of laxatives or enemas indicated	Symptoms causing inability to perform usual social and/or functional activities	Life-threatening consequences, e.g., obstruction, toxic megacolon
Colitis	No symptoms, regardless of pathologic or radiographic evidence of inflammation	Abdominal pain, mucus or blood in the stool	Abdominal pain, fever, change in bowel habits with ileus; peritoneal signs	Life-threatening consequences, e.g., perforation, bleeding, ischemia, necrosis, toxic megacolon
Fever	37.8 – 38.6°C (100.0 – 101.5° F)	38.7 – 39.3°C (101.6 – 102.8° F)	39.4 – 40.5°C (102.9 – 104.9° F)	> 40.5°C (104.9° F)
Fatigue/malaise	Symptoms causing no or minimal interference with usual social and functional activities	Symptoms causing greater than minimal interference with usual social and functional activities	Symptoms causing inability to perform usual social and functional activities	Incapacitating fatigue/malaise symptoms causing inability to perform basic self-care functions
Chills	Symptoms causing no or minimal interference with usual social and functional activities	Symptoms causing greater than minimal interference with usual social and functional activities	Symptoms causing inability to perform usual social and functional activities	NA
Rectal discomfort or irritation	No symptoms or symptoms not	Symptomatic with medical intervention	Symptoms causing inability to perform usual social and	NA

Parameter	Grade 1: Mild	Grade 2: Moderate	Grade 3: Severe	Grade 4: Potentially Life-threatening
	requiring medical intervention	(topical medications / treatments) indicated	functional activities or requiring medical intervention other than topical medications / treatments	
Rectal bleeding	Mild or intermittent without transfusion	Persistent without transfusion	Requires transfusion	Life-threatening consequences

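### The ±20% vital-sign prompt after the enema cannot detect fever: its upper temperature limit lies above the protocol's own Grade 4 cut

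*Protocol*

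**What the plan says.** Protocol 5.4 keeps subjects on site for "at least one hour post-enema administration for vital sign assessment (temperature, heart rate, blood pressure, respiratory rate) and observation". Protocol 6.7 repeats the four signs and adds the interval: "temperature, heart rate, blood pressure, respiratory rate) about every 15 minutes". It then gives the only numerical trigger in that section for the period after dosing: if the subject's "vital signs do not return to the pre-administration values ± 20%, assess the subject for a possible AE". The next step in 6.7 is to complete the visit procedures and send the subject home. Neither section exempts temperature or gives it a separate limit.

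Elsewhere the protocol treats fever on absolute cuts. Table 7-1 in Section 7.7 puts Grade 1 at "37.8 – 38.6°C (100.0 – 101.5° F") and Grade 4 at "> 40.5°C (104.9° F"). Sections 7.3 and 7.4 list fever from 37.8°C as an anticipated event and as a diary-solicited event.

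**The concern.** A symmetric percentage band suits quantities whose ordinary variation is a sizeable fraction of their level. Heart rate, blood pressure and respiratory rate are of that kind. Body temperature is not: the clinically relevant range spans a few degrees around 37°C, so 20% of the level is far wider than any fever. A percentage of a temperature also depends on the scale, because the zero points of °C and °F are arbitrary.

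What is at stake is narrow. Staff who take a temperature in the observed hour and follow the sentence in 6.7 literally get no prompt from it to assess a fever before the subject leaves. The product is a live microbial suspension made from human stool, and Section 7.3 lists both fever and donor-to-recipient transmission of disease as anticipated events. The readings are being taken for a reason, and the written rule for acting on them should be able to fire.

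**Working it through.** **Inputs.** The ±20% rule and the four signs come from Protocol 6.7. The fever threshold (37.8°C) and the Grade 4 cut (40.5°C) come from Table 7-1. The documents give no pre-enema temperature, so I assume 36.0, 37.0 and 37.5°C and also check 35.0 to 38.0°C.

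**Protocol figures first.** With °F = °C × 9/5 + 32, 37.8°C is 100.04°F and 40.5°C is 104.9°F. Both agree with Table 7-1.

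**Band.** Lower limit = 0.8 × baseline; upper limit = 1.2 × baseline. The rise needed to reach a cut is cut/baseline − 1.

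| Pre-enema temperature | Lower limit (°C) | Upper limit (°C) | Upper limit if 20% is taken in °F | Rise to 37.8°C | Rise to 40.5°C |
|---|---|---|---|---|---|
| 36.0°C (96.8°F) | 28.8 | 43.2 | 116.2°F = 46.8°C | 5.0% | 12.5% |
| 37.0°C (98.6°F) | 29.6 | 44.4 | 118.3°F = 48.0°C | 2.2% | 9.5% |
| 37.5°C (99.5°F) | 30.0 | 45.0 | 119.4°F = 48.6°C | 0.8% | 8.0% |

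For baselines from 35.0 to 38.0°C the upper limit runs from 42.0 to 45.6°C on the Celsius scale (35.0 × 1.2; 38.0 × 1.2) and from 45.6 to 49.2°C if the percentage is taken in °F. Every one of these exceeds 40.5°C. From 37.0°C the margin above the Grade 4 cut is 44.4 − 40.5 = 3.9°C. The lower limits are equally uninformative.

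**Break-even baseline.** The upper limit equals the Grade 4 cut when the baseline is 40.5/1.2 = 33.75°C, and equals the fever threshold when it is 37.8/1.2 = 31.5°C. Taken in °F, the first becomes 104.9/1.2 = 87.4°F, or 30.8°C.

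**Scale.** The same reading, 37.0°C or 98.6°F, yields an upper limit of 44.4°C or 48.0°C according to the unit used. The protocol gives fever cuts in both units and does not say which applies to the percentage.

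**The other signs, for contrast.** Assumed values of 75 for pulse, 120 for systolic pressure and 16 for respiration give bands of 60–90, 96–144 and 12.8–19.2. These are usable limits, so the defect is confined to temperature.

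**The case against.** The strongest reply is that the sentence is one sufficient trigger and not a clearance: it nowhere says that a reading inside the band needs no assessment. The rest of the protocol then covers fever.

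- Section 7.1 says "Investigators should make an assessment for adverse events at each visit and record the event on the appropriate eCRF", and the enema-visit column of Table 6-1 is marked for both adverse events and solicited events.
- Section 7.4 includes fever from 37.8°C under "The following list of anticipated events are solicited from subjects via the Subject Diary". Footnote 2 of Table 6-1 covers the day itself: "Solicited events are collected in the Subject Diary from the day of administration of any study enema". That footnote also asks that a solicited event worse than at screening be considered as a possible adverse event, which is close to the remedy proposed here.
- Section 7.8 encourages an investigator in doubt to enter the finding as an adverse event, and 6.7 asks subjects to call if one begins.

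On this view harm requires trained staff to record a fever and disregard it because one percentage rule did not fire.

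Most of this stands, and it keeps the point small. It does not show that fevers would go unrecorded, and I do not claim that they would. What it leaves open is the observed hour. The subject completes the post-enema diary, and staff review it only at the 1-week visit. The adverse-event bullet in 6.7 sits among the activities done before the enema. The Table 6-1 entries and the Section 7.1 duty carry no temperature trigger. Table 7-1 grades a fever once it has been identified but does not tell staff to assess a reading. None of these makes the ±20% sentence work for temperature.

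**Conclusion.** The concern holds. As written, the ±20% prompt has no practical effect for temperature, one of the four signs it covers. For assumed pre-enema values of 36.0 to 37.5°C its upper limit is 43.2 to 45.0°C, above the protocol's Grade 4 cut of 40.5°C. The only assumption is the pre-enema temperature, and the conclusion is the same for any value above 33.75°C when the percentage is taken in °C, or above 30.8°C when it is taken in °F.

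The consequence is modest: a safety prompt that cannot fire for fever during the observation period, with other routes to recording and investigator judgment still in place. The documents do not allow an estimate of how many fevers would go unprompted. Efficacy, type I error, sample size and the comparison between arms are not affected. It is worth correcting because the correction is so small.

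**What to change.** In Protocol 6.7, restrict the ±20% rule to heart rate, blood pressure and respiratory rate. Add that any temperature of 37.8°C (100.0°F) or more after the enema prompts assessment for a possible adverse event, graded by Table 7-1.

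This changes one sentence, uses a threshold the protocol already has, and removes the dependence on °C or °F. It needs no new measurement, since temperature is already taken about every quarter of an hour. The cost is that a few more Grade 1 readings will be assessed; an assessment does not oblige the site to record an event.
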